2.0 Objectives

2.1 Specific Aim 1: To demonstrate the feasibility of adapted PAT procedures in patients with aphasia and memory impairment. Hypothesis: Adapted methods for PAT administration in patients with aphasia are feasible. Even in the presence of memory disorder detecting a treatment signal is possible.

Specific Aim 2: To demonstrate the feasibility of adapted methods for assessing spatial and motor function and pain in patients with aphasia and memory impairment. Hypothesis: Adapted methods for assessing spatial and motor function and pain in patients with aphasia and memory impairment are feasible.

Specific Aim 3: To demonstrate the feasibility of using information about lesion location from the radiology report to classify frontal vs. nonfrontal lesions. Hypothesis: Lesion classification results from radiology reports and brain mapping methods are consistent, confirming this adaptation provides a clinically

accessible, reliable way to identify brain-based predictors of optimal PAT response in future studies.

2.2 Specific Aim 1: Adapted methods for PAT administration in patients with aphasia are feasible. Even in the presence of memory disorder detecting a treatment signal is possible.

Specific Aim 2: Adapted methods for assessing spatial and motor function and pain in patients with aphasia and memory impairment are feasible.

Specific Aim 3: Lesion classification results from radiology reports and brain mapping methods are consistent, confirming this adaptation provides a clinically accessible, reliable way to identify brain-based predictors of optimal PAT response in future studies.

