In addition, brain physiology and anatomy may also define patient subgroups with better response to specific rehabilitation methods (e.g. non-invasive brain stimulation; Plow et al., 2016; Nouri & Cramer, 2011). Although patients across a range of brain lesion locations may experience treatment benefit from PAT (see Yang et al., 2013 for a review), we and others reported that the presence of frontal lobe cortical lesions predicts optimal response to treatment, and subsequent recovery of functional performance in stroke-induced spatial neglect (Chen et al., 2014; Goedert et al., 2018; Gutierrez-Herrera et al., 2018). These experiments were carried out exclusively in right brain stroke-- no data about brain-behavior relationships in recovery from neglect after left brain stroke, with or without treatment, is available. To develop PAT in future large-scale studies as a multi-target treatment for use in patients with both left brain stroke and right brain stroke, first requires determining whether stratifying patients by frontal lobe lesions reveals differences in treatment benefit. The presence of large differences in PAT response related to lesion location would affect the design and evaluation of PAT for stroke rehabilitation as well as eventual clinical decision-making for assigning PAT to eligible stroke survivors. However, clinicians in rehabilitation settings typically obtain information about lesion location from a patient's medical record. Before guidelines for PAT patient selection can be broadly implemented, we must establish that obtaining information about lesion location from the radiology report, as compared to research-based brain mapping methods, is a feasible and reliable method of categorizing lesions.

3.2 Preliminary Study 1: Members of our team have demonstrated that administration of PAT using standardized methods is feasible and yields therapeutic benefits in right brain stroke (Barrett et al. 2012). Purpose: Expert clinicians who assess and treat invisible disabilities like spatial neglect use a variety of rehabilitation techniques (Chen et al. 2017) depending on barriers present, recovery stage, and characteristics of the deficit. However, clinicians carrying out routine care find a large number of choices for spatial neglect

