Preliminary Study 4: Using brain mapping methods, members of our team have shown that right brain stroke patients with frontal lesions respond optimally to PAT (Chen et al., 2014; Goedert et al., 2018). Purpose: Research with neurologically unimpaired individuals suggests that prism adaptation may stimulate lateralized motor-related spatial systems (Fortis, Goedert, and Barrett 2011) linked to frontal cortical brain networks (Ghacibeh et al. 2007). Thus, the presence or absence of frontal brain lesions may affect PAT response. Methods: We had trained raters categorize patients based on their clinical brain images: as having, or not having, a frontal cortical brain lesion (Chen et al. 2014; Goedert et al. 2018). Results: In both studies, patients with frontal brain lesions experienced a more robust therapeutic response to PAT, based on functional performance testing. Although in the first study, medial temporal structures also appeared to play a role in PAT response, this was not confirmed in the second study. Conclusions: A frontal cortical lesion predicts optimal PAT response after right stroke. However, clinical decision-making based on brain mapping with trained raters is not feasible in the clinical environment. This study will extend this work by determining whether obtaining information about lesion location from the medical record is a feasible, reliable way to identify patients with frontal vs. nonfrontal lesions (Aim 3).

3.3 This study is the first to systematically investigate the feasibility of using adapted PAT treatment procedures and spatial-motor-sensory assessments in left-brain stroke patients with aphasia and memory impairment, as well as clinically-accessible methods for identifying patients with optimal response to PAT. This line of research lays the foundation for a potential paradigm shift in the focus of rehabilitation research to PAT as a multi-target treatment to improve spatial function, adaptive movements, functional independence, and pain-free somatic experience. In addition, this study could change the conventional

structure of stroke rehabilitation trials, most of which have not measured the impact of cognitive treatments on motor function, or vice versa, and do not assess the concurrent effect of either cognitive or motor treatment on pain.

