4.0 Study Endpoints *

4.1 We will assess four key aspects of feasibility of our adapted assessment and treatment procedures: acceptability, implementation, adaptation, and limited efficacy testing (Bowen et al., 2009). See Table 1. Acceptability: We will use the Client Satisfaction Questionnaire (CSQ-8; Attkinson & Zwick, 1982; Larsen et al., 1979) to assess satisfaction and perceived value of PAT. We will use the Credibility/Expectancy Questionnaire (CEQ; Devilly & Borkovec, 2000) to assess the degree to which PAT is believable, convincing and logical (credibility) and the expectations for PAT-induced improvement (expectancy). The CSQ-8 and CEQ have been used in patients with subjective cognitive impairment (Foster et al., 2018). Implementation: We will record attendance and completion rates to determine whether KF-NAP®, WMFT and PAT can be carried out as planned. Adaptation: Each session, study staff will complete checklists from the KF-NAP®, the WMFT, and the KF-PAT™ manual (Chen, 2015) to track assessment and treatment fidelity. Notations will be made when modifications to administration methods are required. For the brain mapping, trained raters will map brain lesions using the method from Preliminary Study 4. Then, a blinded neurologist will classify participants as having “frontal” or “nonfrontal” lesions. Using radiology reports, lesions will be classified as “frontal” based on use of that word or “anterior” “premotor” “prefrontal” or “precentral” or as “nonfrontal” if none of those words are present. Limited Efficacy Testing: To detect the acquisition and maintenance of a treatment signal, we will assess spatial-motor-sensory and functional recovery over 7 weeks (Figure 2). We will assess: 1) Functional disability, measured by activities of daily living using the Barthel Index (Mahoney & Barthel 1965) and cognitive and motor function with the FIM or FONE-FIM; 2) Spatial neglect, measured by the Behavioural Inattention Test-conventional subtest (Wilson et al., 1987) and CBS via the KF-NAP® (Chen et al. 2012); 3) Motor function, measured by the WMFT (Lin et al., 2009); and 4) Pain, measured by the Defense and Veterans Pain Rating Scale (Polomano et al. 2016), which includes numbers along with pictures and colors to facilitate nonverbal rating of pain. Assessments will be administered by a trained examiner.

TABLE 1. Study Endpoints.

Key Area	Aim	Question	Analysis on Outcome of Interest

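### The radiology word rule calls a lesion frontal on the bare word *anterior*, and the documents do not fix whether frontal means frontal cortical on both sides of the Aim 3 comparison

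*Combined protocol and SAP*

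**What the plan says.** The report side of the comparison is defined in protocol section 4.1 (Adaptation) and repeated in the Adaptation paragraph of the SAP: "lesions will be classified as “frontal” based on use of that word or “anterior” “premotor” “prefrontal” or “precentral". All other reports are classed "as “nonfrontal” if none of those words are present".

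The mapping side has two steps in the same paragraphs. First, "trained raters will map brain lesions using the method from Preliminary Study 4". The class is not assigned at that step. It comes afterwards, when "a blinded neurologist will classify participants as having “frontal” or “nonfrontal” lesions".

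Section 3.2 describes the Preliminary Study 4 method as sorting patients "as having, or not having, a frontal cortical brain lesion". The predictor that motivates the aim is worded the same way. Section 3.1 (Goal 2) says that "the presence of frontal lobe cortical lesions predicts optimal response to treatment", and the conclusion of Preliminary Study 4 is that "A frontal cortical lesion predicts optimal PAT response after right stroke".

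Aim 3 in section 2.1 does not mention cortex: "To demonstrate the feasibility of using information about lesion location from the radiology report to classify frontal vs. nonfrontal lesions". The endpoint in Table 1 of both the protocol and the SAP is percent agreement on whether a frontal lesion is present. No threshold, 2x2 table, sensitivity, specificity, kappa or interval is planned.

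**The concern.** *Anterior* is a direction, not a lobe. Because any single listed word is sufficient, the rule classes as frontal any report that uses *anterior* of a nonfrontal site. Read literally, it also classes as frontal a report that uses a listed word only to deny a lesion there.

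The second problem is the target. If the mapping side keeps the cortical category of Preliminary Study 4, an isolated frontal white-matter lesion is nonfrontal by mapping and frontal by report. If the neurologist applies a plain frontal label, the two sides match on that lesion, but neither measures the predictor as the Background describes it. The documents do not say which applies.

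Aim 3 is meant to support a conclusion about the radiology report as an accessible source for picking out likely responders in later studies. The single agreement figure mixes three things: what reports contain, how the word list reads them, and whether both methods use the same definition. The last two can be settled before any data are seen.

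**Working it through.** The documents give no accuracy, prevalence or expected agreement for the rule, so there is no planned figure to reproduce. The check is textual, followed by an illustration.

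**1. Definitions side by side**

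| Place | Target as worded |
|---|---|
| 3.1, Goal 2 | frontal lobe cortical |
| 3.2, Preliminary Study 4, categories and conclusion | frontal cortical |
| 2.1, Aim 3 | frontal |
| Table 1 endpoint (protocol and SAP) | frontal |
| 4.1 and SAP, neurologist step | frontal |
| 4.1 and SAP, report rule | any of five words, no cortical condition |

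The mapping step points back to a cortical method, and the neurologist step that follows it drops the word.

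**2. Size of the false-frontal effect, under assumptions**

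The 30 participants are from section 12.0. All else is assumed: 15 to 18 truly nonfrontal, 10% to 30% of those called frontal by the rule, and no frontal lesion missed.

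- False-frontal calls = truly nonfrontal × false-frontal rate. Low: 15 × 0.10 = 1.5. High: 18 × 0.30 = 5.4.
- Agreement = (30 − false-frontal calls) / 30. Low error: 28.5/30 = 95%. High error: 24.6/30 = 82%.
- Share of report-frontal patients wrongly labelled = false-frontal / (true frontal + false-frontal). Low: 1.5/(15 + 1.5) = 9%. High: 5.4/(12 + 5.4) = 31%.

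**3. Does the rule over-call on balance?**

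Let p be the proportion truly frontal, Se the proportion of those caught, and f the false-frontal rate. The net excess of frontal calls is 30 × [(1 − p)f − p(1 − Se)].

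- p = 0.5, Se = 1, f = 0.1: 30 × (0.05 − 0) = +1.5.
- p = 0.5, Se = 0.9, f = 0.1: 30 × (0.05 − 0.05) = 0.
- p = 0.7, Se = 0.8, f = 0.2: 30 × (0.06 − 0.14) = −2.4.

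The sign depends on inputs that the documents do not give. Step 2 shows an excess because it assumes that nothing is missed.

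**4. Can percent agreement show what went wrong?**

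Take 15 of 30 frontal by mapping and 6 discordant.

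- All six false-frontal (15 both frontal, 6 report only, 0 mapping only, 9 neither): agreement 24/30 = 80%. Chance agreement = (21 × 15 + 9 × 15)/900 = 0.5, so kappa = (0.8 − 0.5)/0.5 = 0.60.
- All six missed-frontal (9, 0, 6, 15): agreement 80%. Chance agreement = (9 × 15 + 21 × 15)/900 = 0.5, so kappa = 0.60.

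Opposite errors give the same agreement and the same kappa. The 2x2 table separates them. The exact 95% interval for 24/30 is 61% to 92%.

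**The case against.** The strongest reply is that Aim 3 tests this very procedure. A simple word rule is part of what would make the method usable in a clinic, and any wrong class will show as disagreement with mapping. This is fair in part: disagreement is a legitimate finding, and it goes too far to say that a low figure would necessarily be an unjust verdict on radiology reports. The reply does not rescue the plan, because percent agreement alone cannot separate a word-list error from a limit of the reports, or show which way the errors run.

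A reader might infer that the rule over-calls frontal lesions on balance. The documents do not support that. They give no rates, and the default to nonfrontal can miss a frontal lesion described in other words.

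A reader might also infer that a mismatch between a cortical reference and a non-cortical report rule is established. It is not. The Preliminary Study 4 method is invoked for mapping the lesions, and the neurologist's label that follows carries no cortical restriction. A frontal white-matter lesion could be called frontal on both sides. What stands is that the definition is left open.

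Nor is *anterior* without value. It may capture a frontal lesion described only by arterial territory, so qualifying it trades some sensitivity for specificity.

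Finally, the consequences within this study are limited. Aim 3 is the secondary objective in section 1.0, the analysis is descriptive, no agreement threshold is set, and section 6.1 plans PAT for both groups without reference to lesion class.

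**Conclusion.** The point holds in a limited form. As written, the rule permits false-frontal calls, because *anterior* counts in any context. The target of the comparison is stated as frontal cortical in the Background and as frontal elsewhere, so the two methods may not be classifying the same thing. Neither the frequency nor the net direction of the resulting errors can be known from the documents. The range of 1.5 to 5.4 false-frontal calls, with agreement of 95% down to 82%, illustrates what the assumed rates imply and is not an estimate. It rests on a 10% to 30% false-frontal rate and on no missed frontal lesions. This is a cheap improvement to a secondary feasibility aim, worth making before the reports are classified.

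**What to change.** Amend section 4.1 and the SAP as follows.

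(a) Count *anterior* only where the report ties it to the frontal lobe or to a frontal arterial territory. Apply all five terms only to affirmative descriptions of the index left-hemisphere lesion, so that denied or incidental mentions do not count.

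(b) State one definition of frontal for both the mapping classification and the report rule. It should be cortical if it is to match the predictor in sections 3.1 and 3.2. Fix in advance how to code a report that names a frontal lesion but is silent on cortex, for example as frontal, with the opposite coding as a sensitivity result. Without such a rule, a cortical definition would leave some reports uncoded.

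(c) Report the 2x2 table of report class against mapping class beside percent agreement, and give agreement under the current word list as a sensitivity result.

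The cost is protocol and SAP wording, and reading about 30 reports in context, with somewhat more judgement than a bare word rule. A few frontal lesions described only as *anterior* may be missed. The sensitivity result under the current list would show the effect of that. No participant visits or assessments are added.

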Acceptability	1	
• Do left brain stroke patients view PAT as a satisfactory and credible tool for rehabilitation?	
• Range of post-PAT satisfaction ratings on CSQ-8• Range of credibility and expectancy ratings on CEQ (pre and post PAT)
Implementation	1,2	
• Can KF-NAP®, WMFT, DVPRS and PAT be implemented as planned in left brain stroke patients?	
• Completion rate for KF-NAP®, WMFT, DVPRS and full 10-session PAT
Adaptation	1,2,3	
• What modifications are necessary for implementation of KF-NAP®, WMFT and PAT in left brain stroke patients?• Is classification of lesion location from the medical record consistent with classification using brain mapping?	
• Number and type of modifications to KF-NAP®, WMFT and PAT protocol• Percent agreement on presence or absence of frontal lesion between radiology report and brain mapping
Limited Efficacy Testing	1,2	
• Is there promise for application of PAT in left brain stroke patients?	
• Visual inspection of recovery trajectories on spatial-motor-sensory and functional assessments over 7 weeks to detect the acquisition and maintenance of a treatment signal

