10.3 N/A

10.4 N/A

11.0 Vulnerable Populations* N/A

11.1 N/A

12.0 Local Number of Participants

12.1 30

12.2 Based on attrition rates in our previous studies, we expect ~20% of participants will not complete the study. Thus, we will need to enroll approximately 36 participants to achieve the target sample size of 30. We anticipate needing to screen approximately 100 patients in order to meet our target sample size.

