Adaptation	
 What modifications are necessary for implementation of KF-NAP®, WMFT and PAT in left brain stroke patients? Is classification of lesion location from the medical record consistent with classification using brain mapping? 	
 Number and type of modifications to KF-NAP®, WMFT and PAT protocol Percent agreement on presence or absence of frontal lesion between radiology report and brain mapping
Limited Efficacy Testing	
 Is there promise for application of PAT in left brain stroke patients? 	
 Spatial-motor-sensory and functional assessments over 7 weeks to detect presence of a treatment signal

Table 1. Key areas of feasibility and related data analysis.

Acceptability: We will use the Client Satisfaction Questionnaire (CSQ-8; Atkinson & Zwick, 1982; Larsen et al., 1979) to assess satisfaction and perceived value of PAT. We will use the Credibility/Expectancy Questionnaire (CEQ; Devilly & Borkovec, 2000) to assess the degree to which PAT is believable, convincing and logical (credibility) and the expectations for PAT-induced improvement (expectancy). The CSQ-8 and CEQ have been used in patients with subjective cognitive impairment (Foster et al., 2018).

Implementation: We will record attendance and completion rates to determine whether KF-NAP®, WMFT and PAT can be carried out as planned.

Adaptation: Each session, study staff will complete checklists from the KF-NAP®, the WMFT, and the KF-PAT™ manual (Chen, 2015) to track assessment and treatment fidelity. Notations will be made when modifications to administration methods are required. For the brain mapping, trained raters will map brain lesions using the method from Preliminary Study 4. Then, a blinded neurologist will classify participants as having “frontal” or “nonfrontal” lesions. Using radiology reports, lesions will be classified as “frontal” based on use of that word or “anterior” “premotor” “prefrontal” or “precentral” or as “nonfrontal” if none of those words are present.

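### Applied literally, the five-word radiology rule for Aim 3 can label a report nonfrontal when it names a frontal site in unlisted terms, so percent agreement may understate what the report can show

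*Combined protocol and SAP*

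**What the plan says.** Section 4.1 (Adaptation) gives the rule for radiology reports: "lesions will be classified as “frontal” based on use of that word or “anterior” “premotor” “prefrontal” or “precentral". The same sentence ends with the default category for every other report: "precentral” or as “nonfrontal” if none of those words are present". The Adaptation paragraph of the SAP repeats the rule. Neither place mentions word stems, compounds, synonyms, an indeterminate class or adjudication, and neither says who applies the rule.

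The comparator has no vocabulary limit. Trained raters map the lesion by the method of Preliminary Study 4, and the next step is: "Then, a blinded neurologist will classify participants as having “frontal” or “nonfrontal” lesions".

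The Aim 3 outcome in Table 1 of both the protocol and the SAP is "Percent agreement on presence or absence of frontal lesion between radiology report and brain mapping". The hypothesis in section 2.0 is that "Lesion classification results from radiology reports and brain mapping methods are consistent". No agreement threshold, kappa or confidence interval is planned, and section 17.1 and the SAP describe the analysis as descriptive.

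**The concern.** Aim 3 asks whether the information in a radiology report is good enough to sort patients into frontal and nonfrontal groups. The rule tests something narrower: whether one of five particular words occurs. The two come apart when a report names a frontal site in other words.

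The list omits the combining form fronto-, which names the frontal lobe in compounds. It counts precentral and premotor cortex as frontal but omits 'motor cortex' and 'supplementary motor area', which are frontal motor regions of the same kind. A report relying only on such terms gets a label that contradicts its content. If the neurologist classifies the mapped lesion as frontal, the participant is scored as a disagreement, and percent agreement cannot show whether the report or the word list caused it.

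Section 3.1 says the reliability of report-based classification must be established before guidelines for selecting patients for prism adaptation can be broadly implemented. A shortfall due to vocabulary could be taken as a weakness of the report. A rule carried forward unchanged could also place some frontal patients in the nonfrontal group in later studies.

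**Working it through.** **Plan's own figure.** None to reproduce: the documents give no expected agreement, threshold or power for Aim 3.

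**Step 1: apply the rule to example phrases.** The five words were matched as whole words and as letter strings. The phrases are illustrative; the documents contain no report text.

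| Report wording | Whole word | Letter string |
|---|---|---|
| left frontoparietal infarct | nonfrontal | nonfrontal |
| left frontotemporal infarct | nonfrontal | nonfrontal |
| left fronto-insular infarct | nonfrontal | nonfrontal |
| infarct in left motor cortex | nonfrontal | nonfrontal |
| left supplementary motor area | nonfrontal | nonfrontal |
| Broca's area infarct | nonfrontal | nonfrontal |
| left orbitofrontal infarct | nonfrontal | frontal |
| left inferior frontal gyrus | frontal | frontal |
| frontoparietal infarct involving precentral gyrus | frontal | frontal |
| left MCA infarct, anterior division, frontoparietal | frontal | frontal |

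The letters 'fronto' do not contain 'frontal', and 'motor' does not contain 'premotor'. The last two rows show that any listed word elsewhere in the report removes the problem.

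**Step 2: cost per case.** Section 12.2 gives the denominator: "we will need to enroll approximately 36 participants to achieve the target sample size of 30". With N = 30, one discordant participant costs 1/30 = 3.3 points. Agreement is (30 − k)/30: k = 1 gives 96.7%, k = 3 gives 90.0%, k = 6 gives 80.0%.

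**Step 3: range under stated assumptions.** Let p be the share frontal on mapping and m the share of those whose report uses only unlisted terms. The documents give neither, so I take p as 30–70% and m as 0–30%. With no other source of disagreement:

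- participants miscalled = 30 × p × m
- agreement = 1 − p × m

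| p | m = 0 | m = 10% | m = 20% | m = 30% |
|---|---|---|---|---|
| 30% | 100% (0) | 97% (0.9) | 94% (1.8) | 91% (2.7) |
| 50% | 100% (0) | 95% (1.5) | 90% (3.0) | 85% (4.5) |
| 70% | 100% (0) | 93% (2.1) | 86% (4.2) | 79% (6.3) |

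Expected agreement, with participants miscalled in parentheses.

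**Step 4: make-up of the nonfrontal group.** The truly frontal share of those labelled nonfrontal is p × m / (1 − p × (1 − m)). At p = 50%: 0.05/0.55 = 9% for m = 10%, 0.10/0.60 = 17% for m = 20%, and 0.15/0.65 = 23% for m = 30%.

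**Step 5: errors the other way.** The rule also calls 'anterior temporal lobe infarct' and 'no frontal lesion; left occipital infarct' frontal. If a share f of nonfrontal cases is called frontal, agreement = p(1 − m) + (1 − p)(1 − f). At p = 50%, m = 20%, f = 10%, this is 0.40 + 0.45 = 85%, against 90% with f = 0. The two errors pull the frontal rate in opposite directions, but both lower agreement.

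**The case against.** The strongest reply is that literal matching is an inference. The rule speaks of use of a word and mentions no software, so a human reader might count 'frontoparietal' as use of 'frontal'. That is fair. Listing 'prefrontal' beside 'frontal' suggests whole-word matching, since it would be redundant under letter-string matching, but does not settle it. The reply does not reach 'motor cortex' or 'supplementary motor area', which have no listed word inside them. If readers may decide either way on compounds, the rule is not reproducible and the same sentence still needs repair.

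Three stronger readings are tempting, and the documents do not support them.

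- A reader might infer that every frontoparietal or motor-cortex lesion would be mislabelled. The miscall occurs only when no listed word appears anywhere in the report.
- A reader might infer that the agreement figure would be wrong. It would correctly describe the rule as written; the risk lies in taking it as a measure of what report content can show.
- A reader might infer that Aim 3 could reject the radiology report as a source. No threshold exists by which it could do so, Aim 3 is the secondary objective in the Study Summary, and the analysis is descriptive.

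It is also fair that not every lesion reported as frontoparietal will map as frontal. Preliminary Study 4 (section 3.2) used the category of a frontal cortical lesion, so a report of frontoparietal white matter change could be nonfrontal by that standard.

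**Conclusion.** The point holds as a gap in a stated rule. Read literally, section 4.1 and the SAP give a nonfrontal label to a report that names a frontal site only in unlisted terms, and nothing elsewhere in the documents repairs this. The consequence is that percent agreement, the only Aim 3 outcome, may understate how well report content identifies frontal lesions.

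The firm part of the size is 3.3 points per case at N = 30. The number of cases is unknown and may be zero. The 79–100% range rests on assumed values of p and m and on no other disagreement. No net direction can be claimed for the frontal rate, because the rule also errs the other way. The change is worth making because it affects the sole Aim 3 measure and costs very little.

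**What to change.** In section 4.1 and the SAP, keep all five words and add as positive terms:

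- any compound with fronto- or -frontal (for example frontoparietal, frontotemporal, fronto-insular, orbitofrontal);
- motor cortex and supplementary motor area;
- Broca's area, if the investigators agree.

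Fix the list before any report is compared with its map. Report agreement under the present five-word list as a sensitivity result.

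The cost is one sentence in each place, with no new data, staff or procedures. The small downside is that some added terms, such as frontoparietal white matter, could be called frontal when mapping finds no frontal cortical lesion. Setting the two agreement figures side by side would show this. Whether 'anterior' should stay on the list is a separate question, and this change leaves it as it is.
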